4. Safety laboratories should include CBC with differential: chemistry to include parameters listed in [Section 12.1.6.3](#); hematology to include parameters listed in [Section 12.1.6.1](#); coagulation to include parameters listed in [Section 12.1.6.2](#). Cytokine laboratories IL-2, IFN $\gamma$ , IL-6, IL-10, and TNF $\alpha$ . Serum biomarkers CA-125 [ovarian], CA19-9 [PDAC] or CEA [CRC]. Details for central laboratory sample collections are provided in the Central Laboratory Manual
5. ctDNA blood testing will occur at a central laboratory. Details for blood collection are provided in the Central Laboratory Manual
6. The leukapheresis sample may be collected -7 days or +3 days from Visit 9. The PBMCs may be used for immunogenicity and/or biomarker genetic sequencing. Details for central laboratory sample collections are provided in the Central Laboratory Manual.

7. The PBMCs may be used for immunogenicity and/or biomarker genetic sequencing. Details for central laboratory sample collections are provided in the Central Laboratory Manual.
8. If new lesions are observed on radiographic imaging, a standard of care biopsy may be performed per iRECIST criteria to confirm disease progression and when the investigator judges that tissue can be safely obtained. If there is sufficient tissue obtained from the biopsy, the pathology lab should perform in situ gene expression and/or IHC for evaluation of tumor infiltrating T cells and the tumor microenvironment.

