Subjects will receive SC injections of ELI-002 2P during the Immunization Period at Visit 3 through Visit 8. Three months after the Immunization Period, subjects will receive SC injections of ELI-002 2P during the Booster Period at Visit 12 through Visit 15.

The doses evaluated in the Phase 1 cohorts are as shown in Table 1. All cohorts will enroll RAS mutated PDAC, CRC, non-small cell lung cancer (NSCLC) and other solid tumors (including ovarian, bile duct and gallbladder carcinoma).

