#### 9.1.2 Phase 1 Secondary Endpoint

- To report the proportion of subjects with ctDNA reduction and clearance, defined as reduction or clearance in ctDNA compared to baseline, or if ctDNA was not detectable at baseline, serum tumor biomarker (such as CA19-9, CEA, and CA-125) reduction and clearance compared to baseline

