**Table 8: Derived variables**

Variables	Formula
Demographic and Baseline characteristics	
Body mass index (BMI) (kg/m  )	weight (kg)/[height (m)] 
Derivation of Duration	
Study day at any visit	Date of interest – date of first dose of study treatment. One day is added if this difference is ≥ 0
Duration of study (Days)	(Date of study completion/discontinuation (for discontinued subjects) – date of first dose) + 1
Duration of Exposure to the study treatment ( weeks )	Is [last date of booster dose – first date of immunization dose] + 1] / 7. IF treatment discontinuation, then last date of booster dose = last dose date prior to or at the date of treatment discontinuation.
Treatment Exposure and Compliance	
Cumulative Planned volume (mL)	Total planned volume for each dose* Planned number of doses for the duration of exposure
Cumulative actual volume administered (mL)	Total actual volume administered from exposure CRF page (Cumulative value of 'Actual volume administered' from Study Drug Administration)
Expected Dose	Calculated as the expected number of vaccinations multiplied by assigned dose in mg
Compliance (%)	(Cumulative actual volume administered /Cumulative planned volume)*100
Dose intensity (DI) for ELI-002 Amph-Peptides 2P	Amount of actual cumulative dose of ELI-002 Amph-Peptides 2P (mg) divided by expected dose given for a full 10 course of vaccinations.
Dose intensity (DI) for ELI-002 Amph-CpG-7909	Amount of actual cumulative dose of ELI-002 Amph-CpG-7909 (mg) divided by expected dose given for a full 10 course of vaccinations.
Relative dose intensity	Cumulative dose received divided by expected dose and multiplied by 100
Baseline Derivations	
Baseline value	Unless otherwise specified, the baseline value is defined as the last non-missing observation prior to administration of the first dose of study treatment. For most assessments, this would be the Visit 3 value. If Visit 3 is missing, the Visit 2 value will be used.
Change from baseline	Post baseline value – Baseline value
Fold change from baseline	(Post baseline value – Baseline value)/Baseline value
Biomarker Reduction/Clearance	
Note: All reporting will select the biomarker (ctDNA, CEA, or CA-19) which contains the best (i.e., largest decrease post-baseline) result per subject. If there is no decrease for a given subject, then “best” is the smallest increase.	

**Final Analysis  
Statistical Analysis Plan (SAP)**

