
Clearance
	
Define as the percent change from baseline of the on-study ctDNA, or CA19-9, or CEA that achieved -100%.
 
Notes:
 
 
a. Clearance start will be the date of first clearance.
 
b. Once clearance start date is identified for a biomarker, the same biomarker will be used to determine the clearance end date.
 
c. Results will not be considered if a subject has already started taking subsequent anti-cancer therapy.
 
d. If there is a tie for best response across biomarkers, select ctDNA first.                             
 
▪ For PDAC subjects, select CA19-9 second, CEA third.
 
• For CRC subjects, select CEA second, CA19-9 third.
 
 
 

Reduction
	
Defined as the percent change from baseline of the on-study ctDNA, or CA19-9, or CEA that achieved any decrease (i.e., a negative percent change from baseline).
 
Notes:
 
 
a. Reduction start will be the date of first reduction.
 
b. Once reduction start date is identified for a biomarker, the same biomarker will be used to determine the reduction end date.
 
c. Results will not be considered if a subject has already started taking subsequent anti-cancer therapy.
 
d. If there is a tie for best response across biomarkers, select ctDNA first.                             
 
• For PDAC subjects, select CA19-9 second, CEA third.
 
• For CRC subjects, select CEA second, CA19-9 third.
 
 
 

Duration of Biomarker Clearance/Reduction
	

Clearance Duration
	
This is confirmed after clearance start by an increase above -100% change from baseline followed by a second increase above -100% at least 1 week afterwards.
 
Notes:
 
 
a. The end date will be the date of the first subsequent increase.
 
b. If the increase cannot be confirmed by a second increase, then the potential end date of biomarker clearance will proceed to the next increase and so on.
 
c. Subjects with confirmed clearance duration will not be censored.
 

Reduction Duration
	
This is confirmed after reduction start by an increase above the initial reduction followed by a second increase above the initial reduction at least 1 week afterwards.

**Final Analysis  

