**13.8.2 Pharmacodynamics/immunogenic response analysis**

The pharmacodynamic response to ELI-002 2P will be assessed by evaluation of immunogenic responses to the vaccine. PD (Pharmacodynamic) /Biomarker Evaluable Set will be used for tumor biomarker and PD endpoints. Safety analysis set will be used for other summary tables.

A subject level listing will be provided for all immunogenic responses listed in Table . Summary tables will be provided for the Safety Analysis Set, unless otherwise specified.. In addition a waterfall plot of subject’s best tumor responses on percent change from baseline among ctDNA, and all serum biomarkers CA19-9and CEA will be presented.

Additional analyses of Immunogenicity are beyond the scope of this Statistical Analysis Plan and is specified in a separate addendum attached as an appendix in this document.

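### SAP Table 8 and SAP 13.8.2 derive biomarker reduction, clearance and duration from ctDNA, CA19-9 and CEA only, leaving out the CA-125 that the secondary endpoint names and the schedule assigns to ovarian subjects

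*SAP*

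**What the plan says.** **Endpoint.** SAP 9.1.2 (like Protocol 6.2.2) reports ctDNA reduction and clearance or, where ctDNA was undetectable at baseline, "serum tumor biomarker (such as CA19-9, CEA, and CA-125) reduction and clearance compared to baseline".

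**Derivation.** The note in SAP Table 8 reads "All reporting will select the biomarker (ctDNA, CEA, or CA-19", meaning CA19-9. Reduction is "Defined as the percent change from baseline of the on-study ctDNA, or CA19-9, or CEA that achieved any decrease". Clearance is "Define as the percent change from baseline of the on-study ctDNA, or CA19-9, or CEA that achieved -100" percent. The two duration rows follow whichever marker was selected. Tie-breaks are given for two tumour types only: "For PDAC subjects, select CA19-9 second, CEA third", with the serum markers reversed for CRC.

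**Plot.** SAP 13.8.2 plans a waterfall plot of each subject's best percent change "among ctDNA, and all serum biomarkers CA19-9and CEA will be presented".

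**Population and schedule.** All cohorts take PDAC, CRC, NSCLC and "other solid tumors (including ovarian, bile duct and gallbladder carcinoma"). Inclusion criterion 4 in Protocol 7.1 accepts positive ctDNA, or successive rises in a serum marker, or CA-125 of at least 35 U/mL. Protocol 4.1.4.2 states the same intent for ovarian patients. Footnote 4 of Protocol Table 13 assigns markers by tumour: "Serum biomarkers CA-125 [ovarian], CA19-9 [PDAC] or CEA [CRC"]. The footnotes to Protocol Tables 15 and 16 and SAP Tables 4, 6 and 7 repeat this.

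**Declared changes.** SAP 14.0 lists departures from the protocol. Dropping CA-125 is not among them.

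**The concern.** The SAP names CA-125 in its own secondary endpoint and then leaves it out of the rule that computes that endpoint. The omission recurs in the Table 8 note, in both definitions, in the tie-breaks and in the waterfall text, so it does not look like a typing slip. The endpoint introduces its serum markers as examples, but Table 8 has no such wording: its list is closed and is said to govern all reporting.

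The trial has only one secondary endpoint. An ovarian subject who entered on CA-125 with undetectable ctDNA is the kind of subject for whom the serum fallback was written. Under Table 8 the marker that qualified that subject, and that is scheduled for follow-up, cannot count towards response. Because the change is undeclared, a reader of the study report could not tell a deliberate simplification from an oversight.

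**Working it through.** The plan states no figure on this point, so there is none to reproduce. The check sets the rules side by side and then scales the effect of one subject.

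**Step 1: which markers can count for an ovarian subject with undetectable baseline ctDNA?**

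| Marker | In Table 8? | Usable for this subject? |
|---|---|---|
| ctDNA | Yes | No. Percent change divides by baseline, which is undetectable. If a limit of quantification were substituted (SAP addendum 1.9), the value could not fall below it, so no decrease could be shown. The ctDNA response in addendum 2.2 also requires detectable ctDNA at baseline. |
| CA19-9 | Yes | Drawn at screening (Protocol Table 11). The post-baseline footnotes assign it to PDAC. |
| CEA | Yes | Drawn at screening. The post-baseline footnotes assign it to CRC. |
| CA-125 | No | Drawn at screening and scheduled post-baseline for ovarian subjects, but not used. |

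No marker is both scheduled for this subject and admitted by Table 8.

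**Step 2: how is the subject then handled?** Protocol 13.3.3.2 counts anyone who does not attain a response, for whatever reason, as a non-responder. SAP 13.6.1 makes the full analysis set primary for all efficacy endpoints. SAP 13.8.2, however, assigns tumour biomarkers to the PD/Biomarker Evaluable Set, which under SAP 11.4 requires the relevant blood sampling data. The subject is either a non-responder or excluded; CA-125 affects neither outcome.

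**Step 3: size for one subject.** If the subject responds on CA-125 and is scored a non-responder, the rate falls by 1/n:

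- cohort of 3: 1/3 = 33.3 points
- cohort of 6: 1/6 = 16.7 points
- all planned subjects: 1/18 = 5.6 points

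**Step 4: illustration.** Both the starting rate and k are assumptions. Suppose 9 of 18 subjects respond when CA-125 counts: 50.0% (95% Clopper-Pearson interval 26.0 to 74.0). Let k of those 9 be ovarian subjects who respond on CA-125 only.

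| k | Scored non-responder, (9−k)/18 | Excluded, (9−k)/(18−k) |
|---|---|---|
| 0 | 50.0% | 50.0% |
| 1 | 8/18 = 44.4% (21.5 to 69.2) | 8/17 = 47.1% |
| 2 | 7/18 = 38.9% (17.3 to 64.3) | 7/16 = 43.8% |
| 3 | 6/18 = 33.3% (13.3 to 59.0) | 6/15 = 40.0% |

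A subject who would not have responded on CA-125 changes nothing if scored a non-responder. If excluded, that subject raises the rate instead: 9/18 becomes 9/17 = 52.9%.

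**The case against.** Five arguments limit the point.

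- **CA-125 is still reported.** A reader might infer that the marker is never used. The documents do not support that. SAP 9.1.3 keeps change from baseline in CA-125 among the exploratory endpoints, and SAP 13.1 lists all subject data. The gap is confined to the Table 8 derivations and the waterfall plot. This stands.
- **The footnotes may not be exclusive.** A reader might infer that such a subject cannot be assessed at all. That is not established. Table 8's tie-breaks allow CEA in PDAC and CA19-9 in CRC, so the SAP expects some results beyond the footnotes, and the schedule rows name all three serum markers. An unscheduled CEA or CA19-9 could exist for an ovarian subject. Against this, Protocol 10.3 and 10.5 ask for the marker appropriate to the tumour type. What can be said is that no marker is scheduled.
- **Few subjects are exposed.** An ovarian subject genotyped by the plasma assay is ctDNA-positive at screening, so the main route is tissue genotyping with negative ctDNA. BRCA1/2 and other hereditary syndromes are excluded in ovarian cancer. Protocol Table 7 gives G12D plus G12R as 40 + 3 = 43% of ovarian KRAS mutations, and Protocol Table 8 gives KRAS mutation in 9.6 to 12.5% of high-grade serous tumours. If the spectrum is the same across subtypes, 0.43 × 9.6 = 4.1% to 0.43 × 12.5 = 5.4% of those tumours qualify, and up to 0.43 × 61 = 26% of mucinous tumours. This stands as a limit on likely reach.
- **There may be no ovarian subjects.** Planned enrolment ended in 2Q2023, and the SAP revision that added these definitions is dated August 2024. In an open-label trial its authors could have known the tumour mix, and tie-breaks for PDAC and CRC alone fit a dataset with only those tumours. This is plausible, but no text says so. If it is the reason, it belongs in SAP 14.0.
- **No formal test depends on it.** SAP 13.1 plans none for these analyses. That limits the consequence but does not remove the contradiction in a reported rate.

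**Conclusion.** The contradiction is real and undeclared: the endpoint includes CA-125, and the derivation of reduction, clearance and duration, with the waterfall plot, does not. A ctDNA-negative ovarian subject enrolled on CA-125 would have no scheduled marker for the secondary endpoint and would be a non-responder or excluded regardless of CA-125.

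The 33, 17 and 5.6 point figures are maxima for one subject. They assume that the subject responds on CA-125 and is scored a non-responder. Reading them as the actual bias goes beyond the documents, which do not say how many ovarian subjects were dosed or how many of those were ctDNA-negative. If there were none, the effect is nil. ctDNA-positive ovarian subjects remain assessable through ctDNA. The textual finding is firm; its numerical consequence is conditional on enrolment.

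**What to change.** Choose one of two routes.

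1. **Add CA-125.** Include it in the Table 8 note, in the Reduction, Clearance and duration definitions, and in the waterfall text of SAP 13.8.2. Add an ovarian tie-break line: ctDNA first, then CA-125. In the same edit, reconcile the clearance threshold. Table 8 requires a 100% fall for every marker, whereas Protocol 13.3.3.3 treats a serum marker as cleared once it is at or below the upper limit of normal. Without this, a CA-125 that normalises would still not count as cleared. The cost is SAP wording and one more parameter, already collected, in existing programs.
2. **Declare the omission.** If no ovarian subject was treated, say so in SAP 14.0 and state that CA-125 was dropped from the derivations for that reason. The cost is one or two sentences, with no reprogramming.

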### **13.3.3.2. Analysis of Biomarker Response**

Response will be defined as any subject with a reduction or clearance of biomarker (ctDNA or serum tumor biomarker) compared with baseline [[Tie et al, 2019](#)]. Subjects who do not attain a response for any reason (eg, missing data due to withdrawal) will be counted as non-responders. The subset of subjects with biomarker clearance will also be summarized.

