### **13.3.3.3. Analysis of Duration of Biomarker Response**

Duration of biomarker response (ie, reduction or clearance) will be reported for subjects who meet the biomarker reduction or clearance definitions.

- Duration of biomarker reduction is calculated from the date of the first biomarker blood test with a reduction compared to baseline, until the earliest date of any of the following events: (1) subsequent increase in biomarker; (2) subsequent disease recurrence; or (3) death due to any cause.
- Duration of biomarker clearance is calculated from the date of the first negative ctDNA test or the date when the serum tumor biomarker is  $\leq$ ULN to the earliest date of any of the following events: (1) subsequent positive ctDNA test or subsequent serum tumor biomarker  $>$ ULN; (2) subsequent disease recurrence; or (3) death due to any cause.

If a subject has not experienced any of the events for reduction or clearance, duration of response will be censored on the date of the last biomarker assessment.

Response duration will be summarized for each cohort. Assessment of biomarker response duration is considered supportive of the primary biomarker response analysis and is not considered part of the fixed sequence testing procedure to control overall type 1 error.

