#### 9.1.3 Phase 1 Exploratory Endpoints

- Median RFS, 1-Year RFS, and OS.
- Duration of biomarker (ctDNA or serum tumor biomarker) clearance and reduction, defined as time from the date of the first negative and/or decreased biomarker to the earliest date of any of the following events:
  - Subsequent increased/positive ctDNA
  - Subsequent disease relapse
  - Death due to any cause
- Change relative to baseline in:
  - Serum cytokines IL-2, IFN $\gamma$ , IL-6, IL-10, and TNF $\alpha$
  - PROs: EORTC QLQ-C30 and QLQ-PAN26, QLQ-CR29, QLQ-OV28, QLQ-BIL21 or QLQ-LC13
  - Immunogenicity of ELI-002 determined by magnitude of response and fold-change from baseline, using assays such as ICS, Fluorospot, and/or dextramer+ T cells for subjects with HLA alleles for which dextramer/s is/are available.1
  - Biomarker levels (ctDNA, CA19-9, CEA, and CA-125)
  - Immune cell infiltrate and tumor microenvironment if standard of care biopsies are obtained to confirm disease progression

Immunogenicity analyses are beyond the scope of this Statistical Analysis Plan and is provided as an appendix in this document.

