Statistical Analysis Plan (SAP)**

	
Notes:
 
 
a. The end date will be the date of the first subsequent increase.
 
b. The second increase may be above or below the first subsequent increase as long as it is above the first documented reduction.
 
c. If the increase cannot be confirmed by a second increase, then the potential end date of biomarker reduction will proceed to the next increase and so on.
 
d. Subjects with a confirmed reduction duration will not be censored.
 

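### SAP Table 8 requires a −100% change for a serum marker to count as cleared, where the protocol accepts a value at or below ULN, and its duration rows omit relapse, death and a censoring date

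*SAP*

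**What the plan says.** **Clearance.** SAP Table 8 uses a single rule for ctDNA, CA19-9 and CEA: "Define as the percent change from baseline of the on-study ctDNA, or CA19-9, or CEA that achieved -100" per cent. ULN does not appear. Protocol 13.3.3.3 reads "Duration of biomarker clearance is calculated from the date of the first negative ctDNA test or the date when the serum tumor biomarker is" at or below ULN. Protocol 13.3.3.2 adds "The subset of subjects with biomarker clearance will also be summarized", with no threshold of its own. The secondary endpoint in SAP 9.1.2 turns to serum markers for some subjects: "if ctDNA was not detectable at baseline, serum tumor biomarker (such as CA19-9, CEA, and CA-125) reduction and clearance compared to baseline".

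**Duration.** In Table 8, clearance ends when the marker rises above −100%, "followed by a second increase above -100% at least 1 week afterwards". Reduction ends in the same way, at a confirmed rise above the first reduced value. On censoring, the table states only who is exempt, for example "Subjects with a confirmed reduction duration will not be censored". Protocol 13.3.3.3 ends both durations at the earliest of a marker rise (or return to positive or above ULN), recurrence or death; failing these, "duration of response will be censored on the date of the last biomarker assessment". SAP 9.1.3 also keeps "Subsequent disease relapse" and death as end events.

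**Addendum.** Section 2.2 ends ctDNA response when ctDNA rises or is present. The Listing 7 footnote ends it when ctDNA is detectable or exceeds baseline. Neither names relapse or death.

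**Declared changes.** SAP section 14 sends the ctDNA analyses to the addendum and lists several departures from the protocol. The clearance and duration rules are not among them.

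**The concern.** The trial admits subjects on serum markers alone (Protocol 7.1, inclusion 4b and 4c), and a subject with undetectable ctDNA at baseline can be assessed only on such a marker. If that marker normalises to any value above 0, the protocol counts clearance and Table 8 does not. The subject still counts as a reduction, so the combined reduction-or-clearance response is unchanged, but the separately reported clearance count falls.

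If the duration rows are programmed as they stand, a subject who relapses or dies without a confirmed marker rise has no end event. The omitted events are treatment failures, so the error lengthens duration. With no censoring date, the endpoint cannot be computed for such subjects. There are four SAP texts on duration (9.1.3, Table 8, addendum 2.2 and Listing 7) and no statement of which governs, so different programmers could produce different results.

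**Working it through.** The plan gives no figure to reproduce, so the check compares the rules and then puts numbers in.

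**1. The rules side by side**

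| Item | Protocol 13.3.3.3 | SAP Table 8 |
|---|---|---|
| ctDNA cleared | negative test | −100% |
| Serum marker cleared | at or below ULN | −100% |
| Duration ends at | marker rise/positivity, recurrence, death | confirmed marker rise only |
| Otherwise censored at | last biomarker assessment | not stated |

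SAP Table 16 covers RFS and OS only, and SAP 12.2 names censoring only for progression-free and overall survival. Neither supplies the missing date.

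**2. When does normalisation reach −100%?**
Percent change = 100 × (value − baseline) / baseline. A value equal to ULN gives 100 × (ULN/baseline − 1), which is above −100 for every ULN above 0. For ctDNA the two rules agree if an undetectable result is coded 0.

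Baselines are the inclusion 4c values, CA19-9 90 U/mL and CEA 15 ng/mL. The documents give no ULN, so those below are assumptions.

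- CA19-9, 90 to 20: (20 − 90)/90 = −77.8%. Cleared under the protocol for any ULN from 25 to 50; not under Table 8.
- CA19-9 just reaching ULN: (25 − 90)/90 = −72.2%; (37 − 90)/90 = −58.9%; (50 − 90)/90 = −44.4%.
- CEA just reaching ULN: (2.5 − 15)/15 = −83.3%; (5 − 15)/15 = −66.7%.

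SAP 13.7.2 carries a result reported as below x at x itself. If that laboratory convention also applies to tumor markers (an inference), a result under the assay limit still fails. With assumed limits of 1 U/mL and 0.5 ng/mL, (1 − 90)/90 = −98.9% for CA19-9 and (0.5 − 15)/15 = −96.7% for CEA.

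**3. Duration on the visit schedule (illustrative, no new therapy)**

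ctDNA is cleared on Day 231. Recurrence is dated to the Day 399 CT with ctDNA still negative. ctDNA is positive on Days 483 and 567.

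- Protocol: 399 − 231 = 168 days, ended by recurrence.
- Table 8 alone: 483 − 231 = 252 days, ended by the rise confirmed on Day 567.
- Difference: 252 − 168 = 84 days.

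If the subject instead dies on Day 420 with no positive test and no relapse, the protocol gives 420 − 231 = 189 days with an event. Table 8 alone gives no event and no censoring date.

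**The case against.** Several points can fairly be made for the plan.

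- **The protocol is not uniform.** Its synopsis describes response in terms of reduction or absence of the marker, which sounds closer to −100%, and the ULN text appears only in the duration section. This is so, but absence sets no threshold. Section 13.3.3.3 is the only place where the protocol makes serum clearance operational.
- **The effect is limited and not flattering to the product.** Combined response does not change, the clearance subset is descriptive in a trial planned for about 18 subjects, and Table 8's clearance rule can only lower the count. This stands and limits the consequence; it does not settle which rule applies.
- **The change was logged.** The SAP revision history for Version 3.0 names the biomarker definitions as changed. It gives neither content nor reason, and section 14 remains silent.
- **SAP 9.1.3 can be read as supplying relapse and death,** with Table 8 only describing how a rise is confirmed. That reading restores the end events but not the censoring date, and the table does not say so. The overstatement therefore applies if Table 8 is followed alone.
- **The 84-day gap is conditional.** SAP Table 16 counts recurrence at confirmed progression (iCPD). If the Day 399 scan were unconfirmed, confirmation came on Day 483 and that later date were used, both rules would give 252 days and the gap would be 0. This stands as a limit on the example. The death case does not depend on it.
- **The addendum is the older text and covers ctDNA only.** Section 14 nevertheless still directs ctDNA analyses to it.

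**Conclusion.** The concern holds. Table 8's clearance rule contradicts the protocol for serum markers at any ULN above 0, so that conclusion does not rest on the assumed limits. Following Table 8 undercounts the clearance subset of the only secondary endpoint for subjects whose serum marker normalises without reaching 0. The number affected cannot be given, because the documents do not state how many subjects are assessed on serum markers alone.

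The duration rows contradict both the protocol and SAP 9.1.3, and leave subjects without a confirmed rise with no censoring date. In the illustrative relapse case the overstatement is 84 days if recurrence is dated to Day 399, and 0 if it is dated to Day 483; in the death case Table 8 alone yields no result. The primary safety and MTD endpoints and the combined biomarker response are unaffected.

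**What to change.** 1. In Table 8, define clearance as a negative ctDNA test or a serum marker at or below ULN. State how a subject whose serum marker is already at or below ULN at baseline is handled; inclusion 4b requires rising values, not a value above ULN, so this can occur.
2. End each duration at the earliest of marker rise or return to positivity (with confirmation, if that is kept), disease recurrence, or death from any cause. Otherwise censor at the last biomarker assessment, as in Protocol 13.3.3.3. State which scan dates recurrence and how subsequent anti-cancer therapy enters.
3. Put the same ctDNA duration rule in addendum 2.2 and the Listing 7 footnote.
4. List and justify in section 14 any departure that is intended, including the confirmation rule and the −100% criterion if either is to stay.

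The cost is SAP wording and reprogramming, with no new data. Clearance counts may rise and durations may shorten.
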